## **17. Identified Risks**

The Aviation Medical Risk Management Procedure was used during the development of the protocol. This procedure complies with ISO 14971:2012 and ensures hazards are identified for which risks are assessed, designed out, mitigated, or labeled. Where residual risks remain high, risk/benefit analysis has been conducted.

All identified risks have been designed out, mitigated or disclosed with labeling.

## **17.1. Justification for study given risk/benefit outcomes**

PTNS has been used to treat patients with OAB. It requires that a needle electrode be inserted through the patient's skin to provide stimulation to the tibial nerve near the inner ankle. PTNS therapy is performed in a doctor's office one time a week for a 30-minute session for 12 weeks in a doctor's office. Successful patients are then required to continue therapy at least once a month to maintain success. There have been recent studies that have indicated that stimulating more often may be beneficial. PTNS protocols rely on a toe twitch to confirm the correct placement of the needle at the beginning of the session. Once the therapy session begins stimulation is typically reduced below toe twitch. Thus, in most cases there is no means of objectively confirming nerve recruitment during the therapy session. In those patients where stimulation cannot be increased to the level of a toe twitch, there is no objective confirmation of tibial nerve stimulation.

The current study involves testing a surgery-free and non-invasive wearable bladder modulation system in the home by subjects with OAB. In addition, the System, through sensors incorporated into the modulation garment, provide objective confirmation of tibial nerve activation at the beginning and through the modulation therapy which provides personalized treatment for each patient. The Test Article provides several benefits over PTNS. First, it is wearable eliminating any risks associated with a needle puncture. Second, it allows the patient to perform their therapy in their home, eliminating the need for weekly and monthly travel to a physician's office. Third, it will provide objective confirmation that the active tibial nerve stimulation is automatically adjusting the personalized stimulation level for each subject. The study will involve stimulating for 30 minutes transcutaneously over the tibial nerve, either 1 day or 3 days per week for a total of 12 weeks. The main risks to subjects participating in this study is the potential for skin irritation at the electrode site. We anticipate that the risk of pain in this study to be minimal. In the event of pain, the subject can stop the stimulation or continue at a reduced level. As a result of participating in this study, subjects may experience a temporary reduction in their OAB symptoms. Data collected from this study will help in the development of a new therapy to treat their OAB which may benefit them in the future

This study will compare two treatment frequencies, one session a week or three sessions a week for a 12-week treatment period, followed by an optional additional 21-month long-term follow-up phase. Pre-validation and pre-verification testing were done to ensure system functionality and safety for this study. There were no cadaver or animal model testing done with the Test Article. Voltage tests were done to ensure that the Stimulator would stay within the set voltage parameters. Testing was done to ensure the Test Article could run properly for the full 30-minute treatment duration.

Biocompatible materials were chosen for this system to reduce any allergic reactions.

The risks to subjects participating in this study are minimal. Although subjects may see some temporary improvement, there is minimal benefit in participating in this study. The data collected in this study will be used to support the 510K clearance of the Test Article.

## **17.2. Justification of study design**

Electrical stimulation of peripheral nerves has been used to manage chronic pain, Parkinson's disease, epilepsy, and other neurological disorders. These treatments include placing electrodes over the spinal cord, in deep brain structures, and over nerves in the periphery, etc. Recently, PTNS has been used to treat subject with OAB. PTNS is thought to modify the signals from the bladder to achieve its effect, it usually takes 5-7 weeks for symptoms to change. However, patients respond at different rates. In a review of about 100 patients who responded to PTNS, onset of symptom relief began anywhere between 2-12 weeks after starting treatment. For about 20% of these patients, some symptoms didn't improve until after 8 weeks [1]. However, PTNS therapy is performed only in a doctor's office during weekly visits and requires that a needle-electrode is blindly inserted through the patient's skin near their inner ankle. A non-invasive transcutaneous system that can be used at home will make treatment more accessible and convenient for patients, will help to improve treatment compliance and subject satisfaction and may contribute to better outcomes.

Once subjects meet all eligibility and screening criteria, they will be enrolled in the study. Subjects will be randomized to therapy once a week or three times a week for 12 weeks. Unlike PTNS, the Test Article is fully non-invasive and can be done completely at home, eliminating the need for weekly visits to a medical office. This study is designed to minimize patient and site contact to help reduce possible exposure to COVID 19. The only required in-person office visit would be to conduct EMG screening to confirm eligibility for enrollment and to set up the System for home use, and end of study assessments. To further minimize COVID19 exposure, this protocol enables sites to combine Screening Visit 2 and Visit 1/Baseline in a single office visit.

# **18. Administrative Requirements and Quality Assurance**

## **18.1. Institutional Review Board (IRB) / Ethics Committee (EC)**

Before study enrollment can begin, the Investigator must provide the Sponsor with a copy of the approval notice for the protocol and informed consent forms, signed by the committee Chairperson.

## **18.2. Informed Consent**

Written Informed Consent must be obtained from all subjects or their legally authorized representative before recruitment into the study. All potential subjects must be properly informed as to the purpose of the study and the potential risks and benefits known or that can be reasonably predicted or expected.

The Investigator will retain the original copy of the Informed Consent form signed by the subject and a duplicate will be provided to the subject. Only the consent form approved by the IRB/EC must be used.

### **18.3. Clinical Supplies**

All System components will be labeled as investigational and bear the following statement:

"For Investigational Use Only"

### **18.4. Data Management**

All study data will be recorded on the eCRF EDC system or by using sponsor generated paper CRFs. When applicable, deidentified copies of all paper CRFs must be made available to the Sponsor so that the validity and completeness of the forms can be determined. Where possible all paper CRF and EDC data should originate from a verifiable medical record in source documentation for each subject.

Any corrections to paper CRFs should be made by scoring through the original value with a single line and writing the new value next to the original entry with the designated study staff initialing and dating the new entry. Only the designated study staff may amend or otherwise alter any data entered onto the paper CRF or site source documents. Once a change has been made on the paper CRF and the CRF has been submitted to the data department, no change may be made on the original CRF. All corrections must be made with a Data Clarification Form (DCF) for submission to Aviation data management. Significant changes to eCRF EDC data entries are to be captured on a DCF and will require PI approval or approval by designated study personnel prior to submission to Aviation.

If the reason for the correction is not obvious then, when appropriate, a brief explanation of the reason for the correction should be made. Correction fluids should never be used on any document. Before forwarding copies of completed paper CRFs to Aviation Medical the Investigator or designated study staff should review their completeness, accuracy, and legibility. The Investigator/site must always retain a copy of all completed CRFs in his/her ISF.

Study centers will record all study information in an appropriate source document. The data will then be entered directly into an electronic data capture (EDC) system by completing the eCRF via a secure internet connection. Data entered into the eCRF must be verifiable against source documents at the study center. Any changes to the data entered in the EDC system will be recorded in the audit trail.

The Sponsor will be responsible for activities associated with the data management of this study.

## **18.5. Monitoring**

The Investigator will permit the Study Monitor to visit the Investigational Site at regular intervals to review all the CRFs, study related adjunctive data, and study management. These reviews are for the purpose of verifying the adherence to the protocol and the completeness and exactness of the data being entered as per local requirements. The Study Monitor must be kept informed of all issues pertinent to the study. The Study Monitor will be available to discuss questions regarding adverse events, removal of subjects from the study, conduct of the study or any other questions that should arise. At the final monitoring visit the Study Monitor must resolve any outstanding data deficiencies and retrieve all used and unused Test Articles if applicable.

A detailed monitoring plan will be provided separately from the protocol.

## **18.6. On-site Audits**

The various national regulatory authorities and the Sponsor in the person of a scientifically trained and properly authorized employee may request access to all study records, including source documents, for inspection and copying.

Study centers and study documents may be subject to Quality Assurance audits during the study by the sponsor or its representative. In addition, inspections may be conducted by regulatory authorities at their discretion.

## **18.7. Record Storage and Retention**

Federal laws and GCP requires that a copy of all study records (e.g., Informed Consent documents, source documents, study records, etc.) which support CRFs of this study, must be retained in the ISF of the responsible Investigator for a minimum of two years in accordance with local regulations following notification by Aviation Medical that all Investigations (not merely the Investigators portion) are completed, terminated, or discontinued, or that the Food and Drug Administration or the non-U.S regulatory authority has approved the submission.

If the Principal Investigator retires, relocates, or for other reasons withdraws from the responsibility of keeping the study records, custody must be transferred to a person who will accept responsibility. Aviation Medical or its local sponsor must be notified in writing of the name and address of the new custodian.

## **18.8. Clinical Monitors**

The name, title, address, phone, and fax number of the Study Monitor should be provided to the Investigator and Sponsor and kept in the respective Investigator and Regulatory Binders.

## 19. Publications

Investigator agrees, and will ensure that its Agents likewise agree, that neither shall, without Sponsor's prior written consent, independently publish, publicly disclose, present, or discuss any results of, or information pertaining to, Investigator's activities conducted under this protocol until such multi-center publication is released or twelve months after completion of the Study, whichever is the sooner.

After the events recited in the above paragraph of this protocol, the Investigator and/or its Agents shall then be free to publish or publicly present the results of the Study Subjects enrolled solely at Facilities, provided that the manuscript or abstract proposed to be published or presented shall be submitted to Sponsor at least ninety (90) days prior to submission for publication or presentation. Sponsor retains the right to direct removal of any Confidential Information provided by Sponsor and contained therein other than as required to communicate a scientifically appropriate description of the methods and results of the Study, to protect its rights to any patentable inventions set forth therein and to ensure the accuracy of the information contained in the publication or presentation. The Investigator agrees, and will ensure that its Agents likewise agree, to delete any Confidential Information provided by Sponsor that Sponsor directs should not be published pursuant to this paragraph.

Sponsor supports the authorship criteria established by the International Committee of Medical Journal Editors (ICMJE). According to these guidelines, authorship credit is based only on substantial contributions to: (i) conception and design, or acquisition of data, or analysis and interpretation of data; (ii) drafting of the article or revising it critically for important intellectual content; and (iii) approving of the final version to be published. Neither Investigator nor its Agents qualify to be an author if its contribution consists solely of arranging funding, collecting data or supervising the research group. The Sponsor reserves the right to assign a co-author to any publication or public presentation.

## 21. Protocol Amendment Summary of Changes

Summary of Changes for Protocol Version 1 Dated: 06 JUL 2020 to Version 2 Dated: 07 DEC 2020		
SECTION	DESCRIPTION OF CHANGE	RATIONALE
GLOBAL THROUGHOUT DOCUMENT	Formatting changes and other minor edits, including changes to references for consistency/correction, throughout the protocol, without change to meaning or substance.	Improve document consistency, accuracy, readability, and adherence to necessary style.
TITLE PAGE	Version / Date change.	To reflect the current version of the protocol
TABLE OF CONTENTS	Modified to include addition of Section 8 Long-Term Follow-Up.	To Provide necessary information relating to the long-term follow-up phase of the AMHOAB2001 trial.
SECTION 2 – Protocol Summary	Structure, Method of Assignment, and Study Design sections updated to include information related to the long-term follow-up phase of the AMHOAB2001 study.	To provide information regarding the long-term follow-up phase of the AMHOAB2001 study.
Section 5 – Study Design	Updated to include information related to the long-term follow-up phase of the AMHOAB2001 study.	To provide information regarding the long-term follow-up phase of the AMHOAB2001 study
Section 7 – Methods & Procedures	Updated to include information related to the long-term follow-up phase of the AMHOAB2001 study.	To provide information regarding the long-term follow-up phase of the AMHOAB2001 study
Section 8 – Long- Term Follow-Up Phase	Section added to provide information related to the long-term follow-up phase of the AMHOAB2001 study.	To provide information regarding the long-term follow-up phase of the AMHOAB2001 study
Section 10 – Test Article	Updated pictures for the Stimulator and controller app	To reflect latest design of Test Article
Section 21 – Protocol Amendment Summary of Changes	Section added to Protocol	To provide information regarding changes between Protocol Version 1.0 and Protocol Version 2.0.

## **21. Appendix A- Case Report Forms**

[This Page is left intentionally blank]

# 3-Day Bladder Diary Visit #

Subject ID: \_\_\_\_\_

Subject Initials: \_\_\_\_\_

1. Choose **3 days** (entire 24 hours) to complete this record - they **do not** have to be in a row. Pick days during which it will be convenient to measure **every** void.
2. Begin recording when you wake up in the morning and continue for a full **24 hours**.
3. Make a separate entry each time you **void, leak** or have anything to **drink**.
4. Record each time you notice a leak - please indicate how much using a scale from 1-3 (1=drops/damp, 2=wet/soaked, 3=bladder emptied/voided). Record if you felt an "urge" with the leak (yes or no).

Time of Day	Fluid Intake (oz)	Leak Amount (1-3)	Activity with Leak	Urge with Leak (yes or no)	Comments
7:15 am					
7:45 am	2 oz				
9:00 am		2		Yes	
10:30 am	3 oz	1	Sneezing	No	

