3. Have a pacemaker or implanted defibrillator.
4. Have a documented current or reoccurring Urinary Tract Infection (3 or more in the 12 months prior to enrollment).
5. Current use of a marketed device for treatment of their OAB or incontinence (including but not limited to Interstim®).
6. Have had botulinum toxin treatment for their OAB in the previous 8 months.
7. Current use of TENS in pelvic region, back or legs.
8. Had PTNS treatment within 6 months prior to enrollment.
9. Use of investigational drug/device therapy within past 12 weeks.
10. Current participation in another clinical study.
11. Had within 6 months of enrollment a significant untreated substance abuse disorder or polysubstance abuse disorder stemming from dependency-producing medications, alcohol, and/or illicit drugs.
12. Pregnant or planning to become pregnant within the next 12 weeks.
13. Has scar tissue, metal, or other implant in the target ankle that would interfere with stimulation.
14. Has a neurological disorder that causes abnormal sensations in the lower leg (loss of sensation or allodynia).
15. Has a neurological disorder that affects the bladder or a diagnosis of interstitial cystitis, radiation cystitis, or fistulas.
16. Has a skin condition in the area of the ankle stimulation location that would preclude them from using surface stimulation.
17. Has been diagnosed with incontinence due to neurogenic bladder.
18. Have failed a third line treatment for their OAB because of lack of effectiveness in the last 2 years (PTNS, botulinum toxin, or SNS).
19. Urge incontinence due to stress-predominant mixed urinary incontinence (greater than 60% of the time)
20. Have polyuria (>2500 cc urine output per day)
21. Has urinary retention or incomplete bladder emptying
22. Has symptoms of benign prostatic hyperplasia (BPH) - weak stream, straining, hesitancy or intermittency.

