### **13.2. Analysis of Efficacy and Sample Size**

Using data collected at each of Study Visits 2, 3, and 4, percent change from screening at each time point will be calculated for each patient with respect to frequency of OAB symptoms, including 3-day daily averages of daytime voids, urge events, nighttime voids, and urge incontinent events. The maximum percent improvement across the four symptoms will also be calculated at each time point as a composite endpoint. Percent improvement in daily average total voids relative to an upper normal limit of 8, will also be calculated, and will be bounded below at 0% for patients not achieving improvement and bounded above at 100% for patients achieving or surpassing the upper normal limit of 8. Longitudinal analyses will be performed using repeated measures models to assess and describe trends over time with respect to these endpoints. At individual time points, the one-sample T-test will be performed at significance level  $\alpha=0.05$  within each treatment group and for the pooled study groups to assess the mean percent improvements, with 95% confidence intervals for mean percent improvements also calculated. The percent change endpoints are not likely to have approximately normal distributions, but the sample size is considered sufficient such that mean values will be approximately normally distributed, justifying the use of the T-tests. If there is concern with the distributions, then the Wilcoxon signed rank test will be used as an alternative to the one-sample T-test.

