Sample size is evaluated by the performance of the 95% confidence interval for mean percent improvement percent improvement in daily average total voids relative to an upper normal limit of 8. Log ratios of daily average event frequencies at post-screening time points relative to the daily average event frequencies at baseline, which are mathematically related to the percent changes from baseline, are more likely than percent changes to have approximately normal distributions. If such log ratios are normally distributed so that in both treatment groups the median percent improvement (toward zero) in daily average total voids is 15% and so that 25% of patients will achieve a 50% improvement, then with a total evaluable sample size of 80 patients completing the study, there is an estimated 95.6% power to conclude that the mean percent improvement in daily average total voids relative to an upper normal limit of 8 is 25% or larger using the 95% confidence interval. Within each treatment group of size  $n=40$ , there is an estimated 90.8% power to conclude that the mean percent improvement in daily average total voids relative to an upper normal limit of 8 is 20% or larger using the 95% confidence interval.

Two-sample T-tests performed at a significance level  $\alpha=0.05$  will be used to compare the treatment groups with respect to mean percent improvements in frequency of OAB symptoms, and with respect to results of OAB questionnaires. If there is concern with the non-normality of the distributions of these endpoints, then the Wilcoxon rank sum test will be used as an alternative to the two-sample T-test. Linear models will be constructed as extensions of the one-sample and two-sample T-tests to allow for assessments of mean percent improvements and group comparisons with covariate adjustments.

Frequencies of responders at individual time points and over all time points will also be calculated, where a responder for a given OAB symptom is defined as a subject achieving 50% improvement in frequency, and a responder for the composite collection of OAB symptoms is defined as a subject achieving 50% improvement in frequency for at least one symptom frequency. The treatment groups will be

compared with respect to response frequencies using chi-square or Fisher's exact tests, and exact 95% binomial confidence intervals will be calculated.

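### The 3-day diary, as shown, has no field that marks a void, although total voids decide eligibility and form the endpoint on which the trial is sized

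*Combined protocol and SAP*

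**What the plan says.** - **The diary form (Appendix A, 3-Day Bladder Diary).** Subjects choose three 24-hour days, with the advice "Pick days during which it will be convenient to measure" every void. They make a separate entry for each void, leak or drink. Leaks are graded 1 to 3, and the top grade describes the bladder as having emptied. The columns shown are time of day, fluid intake, leak amount, activity with leak, urge with leak, and comments.
- **The sample rows.** 7:15 am has a time only. 7:45 am has a drink. 9:00 am has a grade-2 leak with urge. 10:30 am has a drink and a grade-1 leak on the same row.
- **Use at screening (Section 7.5).** Daytime voids, nighttime voids, urge events and urge incontinence events are taken from this diary, and only subjects who pass on it go on to EMG testing. Inclusion 6 asks for an average of 10 or more frequency events a day. Section 3 defines frequency as the number of voids per day.
- **Use in the analysis (Section 13.2).** "Percent improvement in daily average total voids relative to an upper normal limit of 8" is calculated for each subject, "bounded below at 0% for patients not achieving improvement" and "bounded above at 100% for patients achieving or surpassing the upper normal limit of 8". The same measure sizes the trial: "Sample size is evaluated by the performance of the 95% confidence interval for mean percent improvement" on it.

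**The concern.** A form that feeds a count endpoint should show, on each row, whether the counted event occurred. Here a void is identified by the absence of anything else. If a subject leaks on the way to the toilet and then voids, one row with a leak grade is a natural way to write it down, and the void cannot then be seen. The 9:00 am sample is of this kind: nothing on it says whether a void followed the leak. A grade-3 leak is ambiguous in the other direction, because it could be read as a leak, a void or both, and no rule settles which.

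The error need not be constant. The number of voids hidden behind leaks moves with the number of leaks, which treatment is meant to reduce. It can therefore differ between baseline and follow-up, and between subjects whose leaks respond and those whose leaks do not. The sizing endpoint divides by baseline voids minus 8, a small number near the entry threshold, so small counting errors become large percentages.

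**Working it through.** **1. The plan's own figures.** Enrollment is 80/(1 − 0.15) = 94.1, matching the stated 94 or so. For power, Section 13.2 assumes normal log ratios with a 15% median improvement in total voids, and that "25% of patients will achieve a 50% improvement". The log-ratio mean is ln 0.85 = −0.1625 and the SD is (ln 0.85 − ln 0.5)/0.6745 = 0.787. The baseline void count is not given, so it has to be assumed. Taking the endpoint as (baseline − follow-up)/(baseline − 8), limited to 0–100%, with success when the lower 95% limit reaches the threshold (20,000 to 60,000 simulated trials per case):

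| Assumed baseline voids/day | Power, n = 80 against 25% | Power, n = 40 against 20% |
|---|---|---|
| 10 | 99.9% | 99.1% |
| 12 | 99.6% | 97.7% |
| 16.5 | 95.5% | 90.9% |
| 20 | 88.3% | 84.6% |
| Stated in the plan | 95.6% | 90.8% |

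A common baseline near 16.5 reproduces both stated figures. These calculations start from an assumed distribution of void ratios, not from the form, so nothing about the diary alters them.

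**2. What the form can count.** Of the four sample rows, one is time-only. By that convention the sample holds 1 void. If every row could also include a void, it holds up to 4. Nothing on the form decides between these.

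**3. Effect on one subject's score.** Assumed, not from the documents: urge leaks fall from 3 to 1 a day, and a share s of them sit on the same row as a void. True voids fall from 12 to 10.

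- True improvement: (12 − 10)/(12 − 8) = 50%.
- Counted baseline at s = 0.5: 12 − 0.5 × 3 = 10.5.
- Counted follow-up at s = 0.5: 10 − 0.5 × 1 = 9.5.
- Recorded improvement: (10.5 − 9.5)/(10.5 − 8) = 1/2.5 = 40%.

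In general the recorded value is (2 − 2s)/(4 − 3s): 50% at s = 0, 1.5/3.25 = 46% at s = 0.25, 40% at s = 0.5, and 0.667/2 = 33% at s = 2/3. At s = 2/3 the counted baseline is 10, just meeting Inclusion 6.

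**4. The direction is not fixed.** If leaks stay at 3 a day with s = 0.5, the same true fall is recorded as 10.5 to 8.5, or 2/2.5 = 80%, because the undercount shrinks the denominator while the limit of 8 stays put.

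**5. Effect on eligibility.** With 3 leaks a day and s = 0.5, a subject with 11 true voids is counted at 11 − 1.5 = 9.5 and falls below 10.

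**6. Effect on the mean.** With the assumed baseline of 16.5, the true mean improvement is 42.4%. Missing 10% of voids (an assumed rate) only at baseline lowers it to 39.2%, and the chance of meeting the pooled criterion to 83.5%. Missing 10% only at follow-up raises the mean to 47.6%. Missing 10% at both gives 44.3%.

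**The case against.** **A column may have been lost in reading the PDF.** The form tells subjects to measure voids yet shows nowhere to put a measurement. The 7:15 am sample illustrates nothing after the time. There is no place for an urge without a leak, although Section 7.5 needs urge events. The diary's continuation page appears with a heading and a pad count but no table. This cannot be excluded, and if the original has a void column the main point falls. It is the less likely reading, because the header and all four sample rows agree on six cells and the numbered instructions explain how to record leaks but not how to record a voided volume.

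**Voids are countable by convention.** This stands in part. A subject who follows the separate-entry instruction produces a time-only row for each void, and diaries are reviewed at visits, so odd rows can be queried. But the form's own 10:30 am sample departs from that instruction, and no counting rule is written down for the reviewer.

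**Stronger readings that the documents do not support.**

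- A reader might infer that subjects with polyuria can enter. No section makes the diary the source for Exclusion 20, and Section 7.3 has the investigator pre-screen against the criteria. All that can be said is that the diary as shown cannot supply urine output and the documents name no other source.
- A reader might infer that falling leaks with unchanged voids show up as worsening on the sizing endpoint. With 12 voids throughout, the count would move from 10.5 to 11.5, but the endpoint is floored at 0%, so both the true and the recorded score are 0%.
- A reader might infer that drinks could be counted as voids by tallying every row. Nothing in the documents suggests anyone would count that way.

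**The rates are assumed, and not every subject leaks.** This also stands. Section 7.6 gives the IIQ-7 only to those with incontinence, so the leak mechanism applies to a subset of unknown size. No difference in error between the two arms is shown.

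**Conclusion.** The point holds, subject to a check of the original form. As shown, the diary has no mark for a void, its own sample combines two events on one row, and a grade-3 leak has no counting rule. Inclusion 6 and the endpoint that sizes the trial both rest on the resulting counts.

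The size depends on rates the documents do not give. In the worked case a true 50% improvement is recorded as 40%, with a range of 50% down to 33% as the share of leaks hiding a void goes from none to two thirds. The bias can also run upward if leaks do not fall. The stated 95.6% and 90.8% power and the enrollment of about 94 are unaffected; what is at risk is the accuracy of the counts to which they will be applied. It is a measurement weakness that is cheap to remove, and it does not show the trial to be invalid.

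**What to change.** Check the original diary form first. If it has no void field:

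1. Add a void yes/no box to every row, and count voids only from that box.
2. State on the form and in Section 13.2 whether a grade-3 leak counts as a void.
3. In the same revision, add a mark for urge without a leak. Sections 7.5 and 13.2 need urge events, and the form records urge only alongside a leak.
4. Replace the sample rows with ones that show a void alone, and a void together with a leak.

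The cost is one case report form revision and slightly more effort for subjects on each row. The sample size is not affected. If some diaries have already been completed on the present form, write down the counting convention used for them and report them separately from those on the revised form.
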